Research Question

How do different ketone supplement types affect blood beta-hydroxybutyrate $(\beta\text{-OHB})$ and blood glucose in healthy individuals?

Objectives

- a) To determine the effect of acute ketone supplementation on blood β -OHB across different types of ketone supplements.
- b) To compare changes in blood glucose following acute supplementation with different types of ketone supplements.
- c) To evaluate the influence of acute ketone supplementation on blood pressure and heart rate across different types of ketone supplements.
- d) To investigate the effect of acute supplementation with different ketone supplements on gastrointestinal discomfort, hunger, and fullness.
- e) To explore supplement acceptability and taste across different ketone supplements.

Hypotheses

- a) All ketone supplements will raise blood β -OHB.
- b) All ketone supplements will lower blood glucose.

This is an exploratory/descriptive pilot study that is designed to inform future research; therefore, we do not pose specific hypotheses as to how the ketone supplements will differ with respect to their effects on the above-outlined objectives.

Background Information

Acute increases in blood ketones (beta-hydroxybutyrate, β -OHB) have been found to temporarily reduce blood glucose [1] but therapeutic application has traditionally been limited due to the need for ketone infusion or severe dietary restrictions to achieve nutritional ketosis. With the recent development of exogenous ketone supplements that can be consumed orally [2], it is now possible to acutely raise blood β -OHB concentration without the need for other nutritional modifications or invasive procedures. In our lab, we have previously shown that acute ingestion of oral ketone supplements potently increases β -OHB and immediately lowers blood glucose [3-6]. These findings suggest exogenous ketones to be a promising therapeutic strategy aimed at lowering blood glucose and improving blood glucose control in individuals with impaired glucose metabolism, particularly individuals with prediabetes or type 2 diabetes [7].

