The first ketone supplements available on the market were in the form of either ketone salts (i.e., β -OHB bound to a mineral salt) or ketone monoesters (i.e., β -OHB bound to a ketone precursor such as butanediol) [2]. Ketone salts can lead to gastrointestinal discomfort in many individuals [8] and ketone monoesters have an extremely unpleasant bitter taste. This makes adherence to a nutritional supplement regimen using ketone salts or monoesters challenging. Since then, new formulations have been developed that differ with respect to ingredients (e.g., include flavouring to mask the bitter taste and improve palatability) and chemical properties (e.g., different precursors and/or types of molecule the β -OHB is bound to). In particular, two new ketone supplements (beta-hydroxybutyric acid and 1,3-Butanediol) have recently become commercially available that promise an improved consumer experience.

However, little is known about the pharmacokinetics of these supplements, which can be expected to differ from the original supplements based on differences in formulation. This, in turn, may affect the glucose-lowering properties of the exogenous ketone supplements. While qualities such as an improved taste and gastrointestinal tolerability are desirable in ketone supplements, it is of importance for the field of research focusing on the therapeutic value of exogenous ketones to establish the effect of these different ketone supplements on blood β -OHB and blood glucose and determine how they compare to the effects of the by now well-established ketone monoester.

The overall aim of this pilot study is therefore to test the β -OHB-raising and glucose-lowering effect of these two new types of commercially-available oral ketone supplements (beta-hydroxybutyric acid and 1,3-Butanediol) in comparison to a ketone monoester, which we have used in our previous studies on ketone supplementation.

Research Method

Experimental design

A double-blind randomized cross-over pilot study in which N = 12 healthy adults will participate in three experimental trials with a different ketone supplement in each trial. Each ketone supplement has FDA GRAS (Generally Recognized As Safe) status as a food additive and is available for online purchase in Canada:

- 1) "KE4" (by KetoneAid)
 - Beta-hydroxybutyrate monoester
- 2) "Kenetik" (by DrinkKenetik)
 - Beta-hydroxybutyric acid
- 3) "Ketone 2.0" (by HVMN)
 - 1,3-Butanediol

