The primary outcome will be total β -OHB as represented by the area under the curve across 4 hours. Secondary outcomes include blood glucose, blood pressure, heart rate, taste and supplement acceptability, hunger and fullness, and gastrointestinal tolerability - all measured across the 240-minute post-supplementation period. Blood samples will be collected via finger prick; blood β -OHB and glucose levels will be measured using the "Keto-Mojo" handheld monitor at baseline and 15, 30, 60, 90, 120, 180, and 240 minutes after ingestion of the ketone supplement.

Visits Summary

The study will involve a total of 3 visits to the laboratory.

Visit 1: Baseline screening & first experimental trial (duration 270 minutes)

Individuals will be recruited by word-of-mouth. Individuals must be able to read and understand English in order to understand the study instructions. On the initial visit, the potential participant will read through the information and consent form, be able to ask any questions, and provide written informed consent. The research lead ([name] Candidate) will ensure that the participant understands the details of the study and consent form.

Inclusion criteria will be: i) over the age of 18; and ii) able to fast overnight. **Exclusion criteria** will include: i) being a competitive endurance athlete; ii) following a ketogenic diet, low-calorie diet, periodic fasting regimen, or regularly consuming ketogenic supplements; iii) being unable to travel to and from the university; iv) being unable to follow the diet instructions; v) being pregnant or planning to become pregnant during the study; vi) having been diagnosed with a chronic disorder of glucose or fat metabolism, including type 2 diabetes, chronic pancreatitis, or gallbladder disease; vii) being unable to read or communicate in English.

Females will complete the menstrual cycle questionnaire to confirm they are in the follicular phase. Anthropometric and physiologic measurements will be collected (height, body weight, waist circumferences, blood pressure) for baseline participant characterization. The research lead will review the dietary record with the participant and confirm the participant is fasted and has refrained from structured exercise and alcohol the day prior.

A baseline finger prick will then be performed before ingestion of the ketone supplement. Another 7 finger pricks will be performed at 15, 30, 60, 90, 120, 180,

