and 240 minutes after ingestion of the supplement. Throughout the 240-minute period, participants will be allowed to do quiet work or perform other sedentary activities (reading, watching a movie). Participants will be asked to complete the questionnaire on gastrointestinal discomfort 60 minutes after ingestion of the supplement, and the questionnaires on hunger and fullness as well as taste and supplement acceptability at the end of the 240-minute post-supplementation period.

At the end of the visit, the participant will be reminded to consume the same diet on the day before the next experimental trial, and to refrain from structured exercise and alcohol consumption in the 24 hours prior.

Visits 2 & 3: Second and third experimental trial (duration 240 minutes)

The second and third experimental trial will be identical to the first visit (except no baseline anthropometric measurements will be performed), with the only difference being the different ketone supplement provided to the participant.

Statistical Analyses

Descriptive statistics (means, SD, and frequencies) will be calculated. Significance will be set at P < 0.05. Data across time will be analyzed in R using a linear mixed effects model with subjects as a random factor and condition and time as fixed factors. Assumptions will be tested using Q-Q plots of residuals. Data with skewed distributions will be log-transformed or non-linear mixed effects models will be used. All participants will be included in the intention-to-treat (ITT) analyses and missing data will not be imputed, per contemporary guidelines with use of linear mixed models [10].

Sample Size

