We will recruit 12 participants to be included in this cross-over study, which has blood β-OHB (as represented by the area under the curve across the 4 hours following ingestion of the supplement) as the primary outcome. A previous pharmacokinetic study exploring the effects of a ketone monoester provided at a dose of \sim 10 g in healthy adults found that blood β -OHB was raised to 1.4 \pm 0.6 mM within 30 minutes, and to an average of 0.5 ± 0.5 mM across the entire 4-hour post-supplementation period [2], which represents an effect size of d > 1.0compared to baseline. Using the outcome data from this study (N = 15) and assuming 80% power with an alpha level of 0.05 and a moderate correlation between repeated measures of 0.5, a total sample size of N = 6 would be sufficient to detect an increase in average blood β-OHB compared to baseline (calculated using G*Power v3.1). In order to allow for a more nuanced evaluation of differences between ketone supplements and to account for any dropouts or missing blood samples, we will recruit 12 participants (aiming for equal males and females), which is in line with the sample size of previous pharmacokinetic studies of ketone supplements [2].

Significance

The results of this study will help determine the effect of different types of ketone supplements on blood β -OHB and glucose. This is a pilot study and it will provide useful data to better answer future research questions and aid in the design of longer-term studies.

Outcome Measurements and Methods

The primary outcome will be total β -OHB as represented by the area under the curve across 4 hours. Secondary outcomes include blood glucose, blood pressure, heart rate, hunger and fullness, gastrointestinal discomfort, and taste and supplement acceptability.

Anthropometric Measures

Waist circumference (cm), height (cm), and weight (kg) will be measured using standard procedures. Body mass index (BMI) will be calculated as kg/m².

Physiological Measures

Resting blood pressure and heart rate will be collected for descriptive purpose and throughout the study visits (at the same time points as blood samples are collected). Before measurements, participants will be instructed to sit quietly and rest for 5 minutes. A finger tip heart rate monitor will track heart rate. Blood pressure will be collected using a cuff around the upper arm, a stethoscope will be placed in the cubital fossa for systolic and diastolic blood pressure.

Blood Sampling

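### The primary 4-hour β-OHB AUC has no stated analysis, and the only stated model understates between-supplement standard errors if visits vary

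*Combined protocol and SAP*

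**What the plan says.** The Experimental design section defines the primary outcome as total β-OHB, "as represented by the area under the curve across 4 hours". The Sample Size section repeats this: "as represented by the area under the curve across the 4 hours following ingestion of the supplement". Readings are taken "at baseline and 15, 30, 60, 90, 120, 180, and 240 minutes after ingestion of the ketone supplement", which is 8 per visit at unequal intervals. Each of 12 participants makes three visits, one per supplement.

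The Statistical Analyses section offers descriptive statistics, a 0.05 significance level and one model for data collected over time: a "linear mixed effects model with subjects as a random factor and condition and time as fixed factors". It does not mention the AUC. It states no visit-level term, residual correlation structure, condition×time term, period term or contrast. Missing data are not imputed, and the reason given is the use of mixed models.

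The Hypotheses section expects that "All ketone supplements will raise blood" β-OHB and that "All ketone supplements will lower blood glucose". On comparisons between products it says "we do not pose specific hypotheses as to how the ketone supplements will differ".

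**The concern.** An AUC is one number per visit, so a model with time as a factor cannot be fitted to it. The analysis of the primary outcome is therefore left open, and so is the handling of a missed reading when the AUC is computed.

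The stated model is not a safe substitute for comparing supplements. Within a person, supplement and visit coincide. Anything that shifts a whole visit (prior diet, length of fast, test strips) enters the difference between supplements. With subject as the only random factor, readings from one visit count as no more alike than readings from different visits, so that variation is missing from the standard error.

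The hypotheses concern each supplement's change from baseline, yet no such contrast is named. At stake is the reading of differences between products, which the pilot is meant to pass on to later studies. The Background Information section says that "little is known about the pharmacokinetics of these supplements, which can be expected to differ from the original supplements based on differences in formulation".

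**Working it through.** **Plan's own figure.** The plan gives none for the AUC comparison. Its only calculated figure, 6 participants, concerns a rise from baseline. It can be reached under standard variants (a one-sided paired t-test needs 8 at d = 1.0 and 6 at d = 1.2) and does not bear on this point.

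**Inputs from the documents.** 12 participants × 3 visits × 8 readings = 288 readings in 36 visits; times 0, 15, 30, 60, 90, 120, 180 and 240 min.

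**Assumed input.** The share *s* of within-subject variance that lies between visits, shown from 0 to 0.5. Set v = s and r = 1 − s. For scale, a visit SD of 0.1 mM with residual SD 0.3 gives s = 0.01/0.10 = 0.10; 0.2 with 0.2 gives 0.50.

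**Comparison of two supplements, constant visit shift, identical true curves.** The subject-only model with condition×time has 11 × 23 = 253 residual df. Of these, 22 have expectation r + 8v and 231 have expectation r:

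- Residual mean square: MS = [22(r + 8v) + 231r]/253
- True SE / model SE, between supplements: √[(r + 8v)/MS]
- True SE / model SE, post-dose mean minus baseline within one supplement (the visit shift cancels): √(r/MS)
- False-rejection rate ≈ 2[1 − Φ(1.969/ratio)]

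Example, s = 0.1: MS = (22 × 1.7 + 231 × 0.9)/253 = 0.970; between-supplement ratio = √(1.7/0.970) = 1.32; rate 13.7%.

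| s | MS | Ratio, between | Rate, between | Simulated | Ratio, within | Rate, within |
|---|---|---|---|---|---|---|
| 0 | 1.000 | 1.00 | 4.9% | 5% | 1.00 | 4.9% |
| 0.05 | 0.985 | 1.17 | 9.3% | 10% | 0.98 | 4.5% |
| 0.1 | 0.970 | 1.32 | 13.7% | 14% | 0.96 | 4.1% |
| 0.2 | 0.939 | 1.60 | 21.8% | 22–23% | 0.92 | 3.3% |
| 0.5 | 0.848 | 2.30 | 39.3% | 39–40% | 0.77 | 1.0% |

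At s = 0.1 to 0.5 the between-supplement standard errors are 1 − 1/1.32 = 24% to 1 − 1/2.30 = 57% too small. The overall test of condition rejects in about 18% to 56–58% of trials. The additive form (288 − 12 − 2 − 7 = 267 df) gives pairwise rates within 1 point of these. One trapezoidal AUC per visit, analysed by subject and condition, with or without period, rejects in about 5% throughout.

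**Visits that scale the response.** With an assumed visit CV of 20–40%, the pairwise rate is roughly 6–33%, depending on the assumed curve, residual SD and whether people's responses also scale. The per-visit AUC model stays at about 5%. A trapezoid contrast from a time-course model with random visit falls to about 3–4%.

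**Hypotheses (a) and (b).** An additive model has one time effect for all supplements. If two rise by R and one by 0, each is reported as (R + R + 0)/3 = 0.67R. With condition×time, each change is estimable.

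**AUC against an equal-weight mean.** The trapezoid weights are 7.5, 15, 22.5, 30, 30, 45, 60 and 30 of 240 min, or 3.1, 6.3, 9.4, 12.5, 12.5, 18.8, 25.0 and 12.5%; an average over times gives 12.5% each. Suppose one product is higher by D at 15 and 30 min and lower by D at 120 and 180 min. The equal-weight difference is 0. The AUC difference is (15.6% − 43.8%) × 240 × D = −67.5 D mM·min.

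**The case against.** The strongest reply is that the error inflation falls where the plan makes no claim. The study is an exploratory pilot, and its only hypotheses concern change from baseline. A reader might infer that the tests of hypotheses (a) and (b) are inflated. They are not: under a visit shift they become conservative. That part of the reply stands and limits the weight. It does not dispose of the point. The plan sets a significance level, aims to compare two new products with the monoester, and justifies 12 participants rather than 6 partly by comparisons between supplements.

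Other stronger readings are also unsupported:

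- That the true error rate is 39%. The documents give no visit share, and at share 0 the rate is 5%. The rate also depends on how visits act, so no single figure carries over to glucose, blood pressure and heart rate.
- That within-visit correlation is ignored altogether. The subject effect gives all 24 readings of a person a common correlation. What is missing is the extra correlation within a visit, and the text does not exclude a richer structure; it states none.
- That hypotheses (a) and (b) cannot be tested. This holds only for a purely additive reading. Naming two factors is often shorthand for a factorial model, and Sample Size mentions a rise from baseline, though not as an analysis.
- That the averaged condition effect will replace the AUC. The plan does not say what will be used.
- That any lost reading leaves an AUC undefined. The trapezoid can bridge 6 of the 8 times; only a lost baseline or 240-minute reading leaves an end open.

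**Conclusion.** The point holds and should be fixed. That the primary outcome has no stated analysis follows from the text alone. That the stated model is anticonservative for comparing supplements is conditional on visits varying. Under a constant visit shift, one pairwise comparison rejects in about 10% of null trials at a share of 0.05 and 39% at 0.5. If visits scale the response, the figure is roughly 6–33%. All these shares and CVs are assumptions. The missing within-supplement contrast is a gap in specification and does not inflate error. The exploratory purpose and the absence of between-supplement hypotheses keep the weight moderate.

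**What to change.** 1. **Primary outcome.** Compute one trapezoidal 0–240 min AUC per visit. Compare supplements with condition and period fixed and subject random, and report differences from the monoester with 95% CIs. Bridge a missed interior reading with the trapezoid over the adjacent times, and write this into the AUC definition so that it sits clearly beside the no-imputation rule. If the baseline or 240-minute reading is missing, leave out that visit's AUC; the mixed model still uses the participant's other visits. Do not change the primary model according to which readings are missing.
2. **Time courses of β-OHB, glucose, blood pressure and heart rate.** Fit categorical condition×time plus period, with random subject and random visit-within-subject.
3. **Hypotheses (a) and (b).** Report each supplement's post-dose mean minus its own baseline. Describe it as a change over time, because no visit lacks a supplement.

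**Cost.** A few sentences and a little analysis work; no new data or participants. Period takes the AUC model from 22 to 20 residual df, which widens CIs by about 0.6% (2.086/2.074 = 1.006). In the time-course model, between-supplement CIs widen by about 1.3 to 2.4 times at assumed shares of 0.1 to 0.5. The standard error alone accounts for 1.32 to 2.30; using t on 20 df (2.086) in place of 253 df (1.969) brings this to about 1.40 to 2.44. This removes false precision and loses no information.

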All participants will provide written informed consent before start of data collection. Following screening and informed consent, eligible participants will participate in three experimental trials of β -OHB supplementation with the order of treatment randomized, balanced, and separated by at least 48 hours. Pre-menopausal women will be tested in the follicular phase (days 3-9) to minimize any potential changes in insulin sensitivity across the menstrual cycle [9]. Participants will be asked to refrain from structured exercise and alcohol on the day before each trial. Furthermore, participants will be instructed to record their dietary intake on the day prior to their first experimental visit, and to consume the same foods and quantities on the days before the subsequent experimental visits. Participants will then be asked to fast overnight (at least 8 hours) and refrain from taking any medications on the morning of the trial.

Upon arrival, a baseline fasting blood sample will be obtained via finger prick. The oral ketone supplement will then be consumed within 5 minutes. The different

supplement types will have an overall similar yet likely distinguishable flavour and will be provided at different volumes (based on the manufacturer's formulation) – however, participants will not be aware which flavour and volume will correspond to which ketone supplement. Furthermore, all supplements will be provided in opaque plastic bottles (labelled with "A", "B", or "C" according to a code that only the principal investigator has access to) such that neither the participant nor the research lead will be able to visually identify the supplement type. Each ketone supplement will be provided at a dose of 10 g active ingredient (i.e., 10 g of betahydroxybutyrate monoester, betahydroxybutyric acid, or 1,3-Butanediol). This is the recommended serving size for the two new ketone supplements to be tested (betahydroxybutyric acid and 1,3-Butanediol) and is in line with a previous pharmacokinetic study that showed a dose of \sim 10 g betahydroxybutyrate monoester to successfully raise β -OHB within 30 minutes [2]. Specifically, this leads to one trial each with:

- 1) 20 mL of "KE4" (i.e.,10 g beta-hydroxybutyrate monoester)
- 2) 237 mL of "Kenetik" (i.e., 10 g beta-hydroxybutyric acid)
- 3) 35 mL of "Ketone 2.0" (i.e., 10 g 1,3-Butanediol)

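### The crossover balances treatment order over three visits, but the stated model has no visit (period) term; adding one is a cheap, minor improvement

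*Combined protocol and SAP*

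**What the plan says.** Experimental design describes "three experimental trials of β -OHB supplementation with the order of treatment randomized, balanced, and separated by at least 48 hours". It does not say how many orders are used; 12 participants divide evenly over three or six.

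Statistical Analyses gives one model, for data across time: a "linear mixed effects model with subjects as a random factor and condition and time as fixed factors". No visit, period or sequence term appears there or elsewhere. Participants are all kept in the analysis and missing data are not imputed. The per-visit β-OHB AUC, which is the primary outcome, has no separate model. With one value per visit the within-visit time factor drops out, leaving condition and subject.

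The Visits Summary puts consent, screening and anthropometry into visit 1, which lasts 270 minutes against 240 for visits 2 and 3. Of the later visits it says: "The second and third experimental trial will be identical to the first visit (except no baseline anthropometric measurements will be performed", with the supplement as the only other difference. Sample Size recruits 12, partly "to account for any dropouts or missing blood samples"; no dropout rate is given.

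**The concern.** A design that balances order treats visit as a possible source of variation. An analysis that then leaves visit out keeps the protection against bias while the data are complete, but gives up the gain in precision. It also loses some of the protection once participants miss visits.

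A visit effect is most plausible for blood pressure and heart rate (objective c). Visit 1 has extra procedures and is the participant's first exposure in the study to eight finger pricks and repeated cuff readings, so readings may run differently from those at later visits. At stake are somewhat wider intervals for the supplement comparisons, an inflated residual SD carried into the design of later studies, and small offsets in the contrasts if the data are incomplete.

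**Working it through.** The plan has no figure of its own on this point. Its stated N = 6 concerns the rise from baseline and does not bear on visit effects.

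**Inputs.**
- From the documents: 12 participants, three supplements, three visits, balanced order, subject random.
- Assumed: six orders with two participants each, one summary value per visit, only visit 1 shifted, and a between-visit correlation r = 0.5. The plan uses 0.5 for repeated measures in Sample Size; applying it between visits is an assumption.
- Also assumed: the size d of the visit-1 shift, in within-person SDs.

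**Complete data: bias.** Each supplement is given to 4 of the 12 participants at visit 1. The shift therefore adds 4d/12 to every supplement mean and cancels from every contrast. Bias is 0.

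**Complete data: precision.**
- Error df without a visit term: 36 − 12 − 2 = 22. With it: 20.
- Within one participant, a shift d at one of three visits contributes d²(1 − 1/3) = (2/3)d² to the sum of squares. Over 12 participants that is 8d².
- Expected error variance, in units of the within-person variance: 1 + 8d²/22.
- The interval-width ratio, without versus with the term, is √(1 + 8d²/22) × 2.074/2.086, using the two-sided 5% t values on 22 and 20 df.

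| d | Error variance | Interval width, no term / term | Type I error, no term | Power for a 1.2-SD contrast, no term |
|---|---|---|---|---|
| 0.25 | 1 + 0.5/22 = 1.023 | 1.005 | 0.042 | 0.785 |
| 0.5 | 1 + 2/22 = 1.091 | 1.038 | 0.037 | 0.766 |
| 1.0 | 1 + 8/22 = 1.364 | 1.161 | 0.021 | 0.685 |

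The last two columns come from 4,000 simulated trials, with subject and supplement fitted as fixed effects. With the visit term the same simulation gives type I error 0.044 and power 0.791, whatever the shift.

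**Dropout.** The worst case for m = 1, 2 or 3 dropouts is that all of them stop after visit 1 having started on the same supplement, say A.
- The 12 − m completers then have A at visit 1 in 4 − m cases, and each other supplement in 4 cases.
- Their within-person contrast of another supplement against A is offset by [4 − (4 − m)]/(12 − m) = m/(12 − m) of the shift. This is also the result with subject as a fixed factor.
- With a random subject intercept, the dropouts' single readings pull the other way, and generalised least squares multiplies the offset by (1 + 2r)/3.
- At r = 0.5 the factor is 2/3:
  - m = 1: (2/3)(1/11) = 0.06
  - m = 2: (2/3)(2/10) = 0.13
  - m = 3: (2/3)(3/9) = 0.22
- At r = 0.3 the three values are 0.05, 0.11 and 0.18. At r = 0.7 they are 0.07, 0.16 and 0.27.

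Enumerating every set of 1 to 3 dropouts, each stopping after visit 1 or after visit 2, confirms these as the maxima. At r = 0.5 the largest of the three contrasts averages 0.05, 0.07 and 0.10 of the shift over patterns, and the signed average is 0. With a visit term, at r = 0.5, the offset is 0 in every pattern.

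**Scale.** Two dropouts in the worst pattern with d = 0.5 give 0.133 × 0.5 = 0.07 within-person SD. The standard error of a contrast with 12 completers is √(2/12) = 0.41 SD.

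**The case against.** The case for leaving the plan alone has real weight.

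- **The visits are close to identical.** Fasting, the exercise and alcohol limits and the 240-minute sampling schedule are shared, and Physiological Measures requires five minutes of seated rest before readings. This stands, and makes a large visit effect less likely. It does not remove familiarisation.
- **Prior-day diet is not a visit-1 difference.** A reader might infer one because participants are "instructed to record their dietary intake on the day prior to their first experimental visit" and copy it later. The same sentence has them repeat the same foods and quantities, so the rule is a control against visit effects.
- **The primary outcome is not shown to be affected.** It is the AUC after a fixed oral dose in fasted participants. The documents give no reason why consent or anthropometry would shift it.
- **The comparisons are not biased as such.** A reader might infer that omitting visit biases the supplement contrasts, or does so whenever anyone drops out. With complete balanced data the bias is zero. With dropout unrelated to supplement, what remains is chance imbalance that averages to zero. It becomes systematic only if dropout depends on the supplement. The Background's remark on the monoester's bitter taste makes that conceivable but does not show it.
- **Larger dropout figures do not describe the planned model.** Treating subjects as fixed gives maxima of 0.09, 0.20 and 0.33. The plan has subjects random, which gives about a third less at r = 0.5.
- **Dropouts are allowed for, not forecast.** Sample Size gives no rate.
- **The variance figures are for one value per visit.** They do not carry over directly to the model of up to 12 × 3 × 8 = 288 readings for blood pressure and heart rate.
- **False positives are not inflated.** The test without the term is conservative, and the study is an exploratory pilot.

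What survives is narrower: the term is absent, any visit effect costs precision, and the remedy is nearly free. Pilot status does not dispose of this, because the plan tests at P < 0.05 and its estimates are meant to inform later designs.

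**Conclusion.** The point holds as a minor one. The design balances visit and the stated model ignores it. With complete data the consequence is lost precision only: error variance up about 2%, 9% or 36% for an assumed visit-1 shift of 0.25, 0.5 or 1.0 within-person SD. With 1, 2 or 3 dropouts a contrast can be offset by at most about 0.06, 0.13 or 0.22 of that shift.

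These sizes rest on two participants per each of six orders, one value per visit, a shift at visit 1 only and, for dropout, a random subject intercept with correlation 0.5. The shift itself is assumed throughout. If there is no visit effect, nothing is lost by the present model. The documents do not support a claim that the primary comparison is biased or that the study's conclusions are at risk.

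**What to change.** In Statistical Analyses, add visit number (1, 2, 3) as a fixed factor for every outcome, including the per-visit β-OHB AUC. In Experimental design, state which orders are used; six orders with two participants each keep visit and supplement orthogonal when the data are complete.

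The cost is a line or two of wording and 2 of 22 error degrees of freedom in the AUC comparison. If there is no visit effect, intervals widen by 2.086/2.074, or about 0.6%. The term pays for itself in interval width once the visit-1 shift exceeds about 0.18 within-person SD, where √(1 + 8 × 0.18²/22) = 1.006. With dropouts it also raises the standard error slightly: at r = 0.5, from 0.310 to 0.313 total SD when two participants on the same order stop after visit 1. No extra data, visits or participants are needed.
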